PROJECT Evaluation of Post-Exposure Sauna

TITLE: Treatment of Firefighters – A Pilot Study

STUDY PROTOCOL

NCT NUMBER: NCT03429348

DOCUMENT DATE: MAY 14, 2018

1) Background

Firefighters are at increased risk of cancer, and both inhalation and dermal routes contribute to overall exposure to carcinogens, including polycyclic aromatic hydrocarbons (PAHs). PAHs can be measured in urine samples so urine sampling has been shown to be a good measurement of exposure to toxicants.

Training fires are performed as part of fire suppression continuing education and/or training events scheduled by fire departments to review or present new departmental concepts in fire suppression activities under closely monitored safety conditions. The National Fire Protection Agency (NFPA) requires fire department to annually test active firefighters for competency in fire suppression. This can be done using training fires.

Two types of structure training fires are flashover and burn room fires. Flashover training fires are fires that simulate the transitional phase of a structure fire between the growth stage and the fully developed stage of a fire. During a flashover, ignition of the room contents are ignited at once, includes smoke, and the entire space is consumed by fire. Burn room training fires simulate fires that burn wood, straw, excelsior, hay, wood pallets, generating enough heat for fire training purposes.

After fighting a fire, the standard operating procedures for fire department require a post-fire rehabilitation to prevent the risk of injury that may result from extended field operations under adverse conditions. At the Fire Department, the rehabilitation consists of: 1) assessment of vital signs; 2) revitalization p rest, hydration, refreshments, and temperature regulation; 3) medical evaluation and treatment of injuries, if needed; 4) transportation for those requiring treatment at medical facilities, and 5) reassignment as needed.

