Sauna post-fire incident exposure detoxification was performed post 9-11 and studied in research published in 2006 by Cecchini, etal., (article attached) but the results of the study are incomplete and were not controlled. Crinnion, 2007, as director of the Environmental Medicine Center of Excellence at the Southwest College of Naturopathic Medicine in Tempe, Arizona, summarized that saunas, "...can be used very effectively for certain cardiovascular problems and as a means to enhance the mobilization of fat-soluble xenobiotics. When saunas are used to reduce blood pressure and enhance blood flow and cardiac functioning, only short sauna sessions (15 minutes) are necessary.

A traditional sauna generates heat by heating rocks to heat the air, adding in steam to heat the skin, and generally operate at 180-190 deg F. An infrared sauna uses light to create heat that warms your body directly without warming the air and operate at lower temperatures, 110-140 deg F. A Mayo Clinic Consumer Health report by [name] A Bauer, MD, accessed 12/21/2017 (attached) reported "...no adverse effects have been reported with infrared saunas."

The purpose of the current study is to determine if treatment in an infrared sauna: a) affects absorption of PAHs as measured by urinary metabolites; and b) changes core body temperature and heart rate. Infrared exposure from the sauna treatment is expected to increase the core body temperature, which may have a detrimental effect on the firefighter performance; heart rate will be used as a measurement of stress. There is sparse literature concerning the subject of using infrared sauna as a post-exposure treatment.

2) Purpose

The purpose of the current study is to determine if post-fire training exercise treatment in an infrared sauna as compared to the standard post-fire treatment:

- a) Affects absorption of PAHs as measured by urinary metabolites. (Aim 1)
- b) Changes core body temperature and heart rate. (Aim2)

These two aims will be achieved by the following objectives:

- a. Coordinating with the Fire Department to recruit and consent firefighters scheduled for training fires to participate
- b. Obtaining 12 hour pre and post-fire urine samples, along with dermal samples.
- c. Monitoring core body temperature and heart rate at baseline, during fire response, and for 8 hours after
- d. Splitting the post-fire post-standard Rehab firefighters into 2 groups: no additional treatment group or sauna rehab group.

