- e. Answering a survey to gather demographic information and information about recent exposures that might affect the results of the urine results and information about their participation in the fire

The results of the biological samples may tell us if sauna post-fire rehab is an effective means for increasing the body's removal of toxic chemicals during post-fire rehab with less than a 102 degree core body temperature increase.

3) Lay Summary (approximately 400 words)

The fire department chosen is a career fire department with approx. 260 active firefighters on staff. They respond to fire incidents and other medical emergencies in a 184 square mile area. They train recruits to become firefighters and annually proving drill training in various skills, such as live fire training. Following live fire responses (including training fires) their standard operating procedure includes a rehabilitation requirement to insure that no firefighter will be permitted to continue emergency operations beyond safe levels of physical or mental exertion (rehab).

They would like to add the use of a sauna post-fire response to their rehab SOP and have supported the UA study team lead by [name] to compare a chemical commonly excreted after firefighting to compare the value of adding sauna to rehab post-fire and monitoring the heart rate and temperature using a core body temperature/heart rate monitor data recorder. Urine will be collected for 12 hours immediately before the scheduled training fire and for 12 hours afterwards.

The core body temperature/heart rate monitor works by having the firefighter swallow a sensor shaped like a pill that the data recorder senses the temperature. The pill passes thru the gut and is removed with bowel movement, approximately in 24 hours, depending on the normal excretion timing of the person. A Polar heart rate belt that is worn around the body in the chest area and records the heart rate/pulse of the person wearing it. The firefighter will swallow the sensor and put on the Polar heart rate belt and the UA study team will start the data recorder before the firefighter enters the training fire and will continue to wear it for up to 8 hours afterwards.

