 - 8. **(For Stage 2 fires only)** The subjects will then be randomized to either an infrared sauna treatment, or no additional treatment following their fire department protocols. The firefighters will be randomized by the UA study team as such: Firefighters will pull a piece of paper out of a helmet; if it says "sauna" they will participate in the sauna treatment. If it is blank, they will participate in no additional post-fire treatment. "Sauna treatment" consists of a firefighter entering the sauna for 20 minutes as soon as the fire department has completed their standard rehab.
 - 9. Following the sauna treatment or no additional treatment time period, dermal wipes of the left calf, arm, and neck will be repeated and the subjects will complete a survey and return to work. The dermal wipe samples will be transported under Arizona Department of Transportation guidelines for transportation of samples to the University of Arizona.
 - 10. Core temperature and heart rate will continue to be monitored for up to 8 hours after training scenario. At the end of the 8 hour period, the firefighter will turn the monitor off by pressing the "stop" button and the "On/Off" button.
 - 11. The subjects will collect all their urine after the fire training for a period of up to 12 hours in the same manner that urine was collected prior to the fire training.
 - 12. End of sampling period: At the end of the sampling period, the UA study team will, again, meet the firefighters at the fire department to collect the data recorder/heart rate monitor data recorder, Polar Heart Rate belt, and urine samples.
 - 13. The urine will be stored at the Medical Research Building at -80 deg C until analyzed for urinary PAH metabolites and potentially other toxicants from the fire, and, dependent on the available budget, similar evaluations may be carried out on the skin wipes. The core

temperature and heart rate data will be downloaded from the data recorder onto a password protected computers and will be analyzed for comparison to the pre-fire data. The personal air monitors will be downloaded in the same manner and analyzed for air quality.

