The fire department's training fire is a required training exercise, but the research concerns the comparison of the post-fire sauna treatment versus the standard (no-sauna) treatment post-fire. The data from the core body temperature/heart rate monitor data recorder will be downloaded within 48 hours and examined for excessive core body temperature rise (above 102 Deg F) by the PI, [name]. The firefighter, after exiting the sauna, will have blood pressure pulse readings taken and documented as part of the fire department's post-fire treatment protocols. Firefighters who do not participate in the sauna treatment will be monitored and the data downloaded in a likewise time period, but the data will not be examined by [name] until the data are analyzed by statistical methods as the standard treatment is not being changed by the study from what the fire department normally performs on its firefighters during their normal annual fire training exercises.

16) Withdrawal of subjects

It will be made clear to the firefighters that their participation is voluntary and that they may withdraw on their own volition at any time. It is not anticipated that the PI or other UA study team members will have to withdraw a subject after the consent and verification of the contraindication form. However, there is potential that the firefighter may become not medically fit for duty for an unrelated reason between the consenting and sampling period. This situation would result in the subject being withdrawn from the study.

In addition, in order to adequately achieve the end total of up to 24 firefighter participating in the Stage 2 exercise, it may become imperative to consent more than 24 firefighters. When the time is reached that 24 firefighters have been evaluated for the Stage 2 training fire testing, additional testing of firefighters who consented but haven't been tested will be stopped and the untested firefighters will be withdrawn from the study.

17) Sharing of results with subjects

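### The protocol's 102 Deg F core-temperature check comes after the sauna and the return to work, and no action is attached to it

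*Protocol*

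**What the plan says.** The Background (section 1) anticipates the effect: "Infrared exposure from the sauna treatment is expected to increase the core body temperature, which may have a detrimental effect on the firefighter performance". Section 2 describes the result of interest as removal of toxic chemicals "with less than a 102 degree core body temperature increase", which I read as a core temperature staying below 102 Deg F.

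In the Sampling Protocol Timeline (section 8), step 8 says that sauna treatment "consists of a firefighter entering the sauna for 20 minutes as soon as the fire department has completed their standard rehab". Step 9 repeats the dermal wipes, after which "the subjects will complete a survey and return to work". Step 10 covers the recorder: "At the end of the 8 hour period, the firefighter will turn the monitor off". Under step 12, at the end of the sampling period, "the UA study team will, again, meet the firefighters at the fire department to collect the data recorder".

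Section 15, on subject safety, says the recorder data will be "downloaded within 48 hours and examined for excessive core body temperature rise (above 102 Deg F") by the principal investigator. For firefighters not given the sauna, the same investigator does not look at the data until the statistical analysis. Blood pressure and pulse are taken after sauna exit under fire department protocols.

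**The concern.** The sauna is the heat exposure that the study itself adds, soon after a live fire, to people who then go back to work. The protocol expects it to raise core temperature and names a value it regards as excessive. That value is not used at either of the two moments when it could change what happens to the participant: entry to the sauna and release to work. It is used only in retrospect, and nothing is said about what follows an exceedance, either for that firefighter or for those in later sessions.

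What is at stake is participant safety. Section 10 covers the sauna only by stating that no adverse effects have been reported, and offers no heat precaution. Section 17 withholds individual core-temperature results from firefighters and states no exception for a high value.

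**Working it through.** The documents give no figure to reproduce and no basis for a risk estimate. The check is on the order of events and on whether any other provision fills the gap.

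**Order of events as written**

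1. Rehab is completed and the firefighter goes into the sauna for 20 minutes (step 8).
2. Wipes, survey, return to work (step 9).
3. Recording runs for up to 8 h after training; the firefighter then switches the recorder off (step 10).
4. Urine is collected for up to 12 h after training (step 11).
5. The study team collects the recorder at the end of the sampling period (step 12).
6. The data are downloaded within 48 hours and examined for values above 102 Deg F (section 15).

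The check is item 6. The events it might have influenced are items 1 and 2.

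**Latest download time.** The inputs are 8 h (step 10), 12 h (step 11) and 48 h (section 15). The start of the 48 hours is not stated, so three readings are possible if the full periods are used:

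- clock starts at exposure: 48 h;
- clock starts at recorder switch-off: 8 + 48 = 56 h;
- clock starts at recorder collection: 12 + 48 = 60 h.

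These are limits on the download. Section 15 sets no separate deadline for the examination, which could come later. Under every reading, the check follows the return to work.

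**People concerned.** Up to 24 firefighters enter Stage 2 (section 6). With an even draw, 24 / 2 = 12 receive the sauna.

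**Does another provision supply a core-temperature criterion?**

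- *Standard rehab (section 1).* It includes vital signs, "rest, hydration, refreshments, and temperature regulation", and medical evaluation if needed. No core-temperature value is given, and rehab precedes the added heat.
- *Post-sauna readings (section 15).* Blood pressure and pulse only, with no limit stated.
- *Monitoring by the study team (section 8, core body/heart rate monitoring).* The stated purpose is to compare return to normal between the groups. After step 5, where the display is used to confirm that recording works, no live reading is required.
- *Withdrawal (section 16).* Firefighters may leave at any time; withdrawal by the team is not anticipated, and no temperature rule is given.

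None of these sets a core-temperature condition for sauna entry or release, or an action for a value above 102 Deg F.

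**The case against.** The strongest reply is that the gap lies partly in a document we cannot see. Sauna entry follows the department's completed rehab, and section 3 says the purpose of that procedure is to keep firefighters from continuing beyond safe levels of exertion. Section 4 makes department personnel responsible for safety in the training exercise, and the readings after the sauna belong to department protocols too. This stands in part: those procedures may hold temperature limits. But section 4 speaks of the training exercise, not the sauna, and the 102 Deg F value is the study's own.

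A second reply is that the exposure is modest: a single 20-minute session in a type of sauna described as running at 110-140 deg F, in active firefighters free to withdraw. This bears on the likely size of the risk, which the documents do not let anyone estimate. It does not give the check a function.

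A third reply is that safety gates can damage the comparison. If only sauna participants were held back from work, that arm would get extra rest while Aim 2 compares recovery between arms. Delayed entry could also upset the matched wipe times, and stopping a session at 102 Deg F would cut short the temperature course. This objection stands against a one-arm rule. It is why the fix applies the same rule in both arms and leaves mid-session stopping to the investigator.

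A reader might infer that there is no safety check of any kind. The rehab, the post-sauna readings and the right to withdraw show otherwise.

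**Conclusion.** The concern holds as a participant-safety gap. Followed exactly, the protocol applies its own excessive-temperature value only after the sauna and the return to work. It leaves the clock start and the examination deadline open and states no action. The check could at best inform later sessions, and even that is not provided for.

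In size, it touches about 12 of up to 24 firefighters (assuming an even draw), with the latest download 48 to 60 h after the exercise depending on the clock (assuming the full periods are used). Neither number is a risk. A reader might infer that firefighters will often exceed 102 Deg F or are likely to be harmed, but the documents give no frequency for either. A reader might also infer that the randomised comparison is biased. It is not affected by this gap. The finding further assumes that the fire department's procedures, not shown, do not already impose an equivalent core-temperature limit. If they do, the protocol need only cite it and state the action.

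**What to change.** 1. **Section 15.** Require each sauna participant's trace to be downloaded and reviewed before the next sauna session day. State the action for any value above 102 Deg F: medical evaluation of that firefighter, and a pause or shortening of later sessions.
2. **Steps 8-9.** If the recorder display can be read on site, have the study team read core temperature in both arms at the end of rehab, before the draw, and again at the matched post-sauna or no-treatment wipe time. Nobody above 102 Deg F, or above a lower limit set by the investigator, proceeds to the draw or is released to work until below it. The same rule in both arms helps keep rest and wipe timing comparable, though holds may still be more frequent after the sauna and should be logged. This places the draw after rehab, as the Stage 2 text in section 8 does; the Lay Summary has it during rehab and should be aligned.
3. **Analysis and reporting.** Analyse by assigned arm and report sessions delayed or withheld, with reasons.
4. **Stopping mid-session at 102 Deg F** is left to the investigator, because it truncates the Aim 2 temperature course. If used, count the session as an exceedance so that the stop does not hide the result section 2 asks about.

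The cost is a few sentences and at most 24 x 2 = 48 logged readings, taken by a team already present for the wipes from a recorder already carried. Whether the display shows core temperature and can be read at these points must be confirmed; if not, item 1 still stands. The downside is that an unknown number of sessions may be delayed or withheld, which may dilute the sauna contrast.

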After the fire, the firefighter will perform the standard rehab. During this time, the UA study team will randomly select half of the firefighters to and additional sauna rehab and the other half of the firefighters to no additional rehab. Dermal (skin) wipe samples will be taken off the calf, arm, and neck before the fire, before standard rehab, and after sauna/no additional treatment.

If it is available, a personal air monitor will be worn to assess the air quality in the fire. A post-fire survey will be administered to gather demographic information, pre-fire exposure information, job duties in the training fire, and other information.

The UA study team will perform the urine PAH-OH analysis, download the air monitor data (if performed), results of the surveys, skin wipe analysis (if performed), and download and compare the core body temperature and heart rate data between the sauna rehab and the no additional treatment groups.

4) Setting of the Human Research

The recruitment, consenting, and training fire exercises will take place at the fire department's main office, stations, and training centers used to train firefighters to respond to live-fires. The University of Arizona (UA) study team will be responsible for recruiting and consenting interested firefighters and in collecting samples and surveys before and after the training fire. The fire department personnel are responsible for the training and safety of the firefighters with regard to the fire training exercise. At the University of Arizona, data and sample analysis and manuscript writing will be done at Drachman Hall, Office 317C or A241, at the Medical Research Building Lab 130, or Keating Building, Lab 402. The UA study team are trained in human subjects protection, sample collection, processing, transportation, and analysis.

5) Resources available to conduct the Human Research

The fire department has fire training for both flashover and burn room fires as standard operating training exercises. Making space available to the UA study team to recruit, consent, and collect samples has not caused undue problems to their department as is evidenced in their support letter.

The supplies needed for the UA study team's research will be funded by the PI's fixed price complete account, or alternate sources as determined by the PI.

The sauna already belongs to the fire department and it is NOT being purchased for this research.

6) Study Population

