- 2. If the firefighter answered 'no' to all contraindications, the UA study team will instruct the firefighter to swallow the core thermo pill (the sensor will pass through the body and excreted with their normal bowel movement at the subject's normal rate of motility, which is typically 24-36 hours).
- 3. The UA study team will accept the urine sample collection the firefighter began collecting approximately 12 hours before the anticipated start of the fire. If one of the 12 hour urine samples has not yet been collected by the firefighter, a "zero" hour baseline sample will be collected at the time of the scheduled training.
- 4. The Polar heart rate belt will be donned by the firefighter and three dermal skin wipes (calf, arm, and neck) will be collected prior to the firefighter donning the turnout gear.

- 5. When the fire department personnel say that it is time for the firefighter to don their turnout gear, the UA study team will turn on the core body/heart rate monitor data recorder. Next, the UA study team will place the core body/heart rate monitor data recorder in the firefighter's inner pocket of their turnout jacket. The UA study team will make sure the data is recording by pressing the "run" button to see that it registers a digital reading. After the firefighter is in full gear, the placement of the heart rate monitor/data recorder will be accessed for firefighter activity safety (not impeding movement) and a personal air monitor may be attached to the outside of the turnout gear jacket in an unobtrusive location.
- 6. The firefighter will enter the training fire room as instructed by standard fire department protocol for the standard period of time for participation in the training fire. Following cessation of the training fire, the subjects will follow their standard fire department procedures for post-fire treatment (rehab).
 - 7. The UA study team will remove the personal air monitor from the firefighter's turnout jacket (if applicable). The firefighters will remove their turnout gear at this time. The heart rate/core body temperature monitor data recorder will be transferred from the turnout jacket inner pocket to a pants pocket. A dermal wipe (a gauze pad moistened with alcohol) of the left calf, arm, and neck will be obtained prior to cleaning their skin with their standard rehab baby wipes (part of the standard fire department procedures for post-fire treatment.)

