Dermal wipes are 2x4" alcohol wipes. They will be collected by the UA study team from the right calf, right arm, and right neck before the firefighter dons turnout gear (before entering the training room fire.) To collect the samples, the UA study team member will gently wipe the area of the right calf (midway between the back of the knee and the heel) in a 2x4" rectangle gently but firmly in 2 up and down wiping directions. This process will be repeated on the opposite calf, arm, and neck after the fire when the firefighter removes the turnout gear and before the firefighter wipes his skin off with the standard rehab baby wipes, and again right after exit from the sauna (if in the sauna treatment group) or at the same time post-fire (if in the standard treatment group—the no-sauna group.)

9) Cost to subjects

There will be no monetary cost to the subjects. The fire department has given their support for the time required to recruit and consent firefighters individually. The department has also given support for allowing the firefighters the time to participate in the research portions of the training exercise.

10) Risks to subjects

- Biological and Air Sampling: There is no risk to the firefighter to self-collect urine samples or skin wipes, or to wearing a personal air monitor.
- Survey: There are no known risks with filling out survey questions; the firefighters will be informed that any section can be left unanswered if unknown or stressful. Individual participant's answers to the questions will not be made available to the fire department.
- Flashover or Burn Room Training: The fire training itself is a part of the job and is a continuing education event required by fire department for active firefighters. According to NFPA (National Fire Protection Agency) 1001, fire departments must develop recurring proficiency cycles for fighting structure fires with the goal of preventing skill degradation and potential for injury and death of members and an annual skill check to verify minimum professional qualifications of its members. The firefighter may be required by the fire department to have training in the burn room and/or flashover training. If the firefighter is not scheduled for a specific training, the fire department will not schedule them. As documented in the supporting letter from the fire department, there is no risk to the firefighter's job for not participating in the study.

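### Does taking the post-fire and post-treatment skin wipes from the same left-side sites spoil the last wipe?

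*Protocol*

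**What the plan says.** All references are to the protocol.

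- **Three wipe times.** Section 3 (Lay Summary): "Dermal (skin) wipe samples will be taken off the calf, arm, and neck before the fire, before standard rehab, and after sauna/no additional treatment".
- **Wipe 1, before the fire.** The dermal wipes paragraph of section 8 puts it on the right side. Only the calf has a landmark, and staff are to "gently wipe the area of the right calf (midway between the back of the knee and the heel", within a 2x4 inch rectangle.
- **Wipe 2, after the fire.** Section 8, timeline step 7: "A dermal wipe (a gauze pad moistened with alcohol) of the left calf, arm, and neck will be obtained prior to cleaning their skin". The dermal wipes paragraph agrees: "This process will be repeated on the opposite calf, arm, and neck after the fire when the firefighter removes the turnout gear". It sets the time as "before the firefighter wipes his skin off with the standard rehab baby wipes".
- **Randomisation and sauna.** Step 8 follows wipe 2. Firefighters draw lots, and sauna treatment means "entering the sauna for 20 minutes as soon as the fire department has completed their standard rehab".
- **Wipe 3, after the sauna or control period.** Step 9: "dermal wipes of the left calf, arm, and neck will be repeated". The dermal wipes paragraph has the process done "and again right after exit from the sauna (if in the sauna treatment group) or at the same time post-fire".
- **Role of the wipes.** Section 2 lists dermal samples among the objectives, but Aim 1 concerns urinary metabolites and Aim 2 core temperature and heart rate. Section 3 and step 13 of section 8 make analysis of the wipes conditional, step 13 on budget. Section 15 describes the research as a comparison of sauna with standard treatment.

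**The concern.** The side changes between wipes 1 and 2 but not between wipes 2 and 3. On the calf, one landmark and one rectangle make it natural to wipe the same patch twice. On the arm and neck only the side is fixed, so overlap is left to chance. An alcohol wipe removes what it samples. Where the two wipes overlap, wipe 3 would meet skin that the study itself has already partly cleaned.

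Two things would be at stake. Wipe 3 would yield less, with a greater risk of falling below what the assay can detect. The fall from wipe 2 to wipe 3 would also include removal by sampling, which a reader could mistake for removal by rehab or by the sauna. Samples taken this way could not be retaken.

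**Working it through.** The protocol gives no figure on this point, so there is none to reproduce. Skin load, wipe recovery and assay limit are not stated. The values below are assumptions, used only to see what depends on what.

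**Assumed inputs**
- e: fraction of surface PAH removed by one alcohol wipe, 0.3 to 0.9
- f: share of the wipe 3 area already covered by wipe 2, from 0 to 1
- b: fraction removed by the rehab baby wipes, 0.5 or 0.9
- s: fraction of surface PAH removed by the sauna
- x: PAH brought to the surface by the sauna, as a share of the post-fire load

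**1. Yield of wipe 3 relative to unwiped skin: 1 - f·e**

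| Overlap | e = 0.3 | e = 0.9 |
|---|---|---|
| f = 1 | 0.70 | 0.10 |
| f = 0.5 | 0.85 | 0.55 |
| f = 0 | 1.00 | 1.00 |

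The loss runs from nothing to 90%, and the protocol does not say where in that range the study would lie.

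**2. Fall from wipe 2 to wipe 3 with no sauna effect**

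On a re-wiped patch the fall is 1 - (1-e)(1-b). On unwiped skin it is b.

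| | Re-wiped, e = 0.3 | Re-wiped, e = 0.9 | Unwiped |
|---|---|---|---|
| b = 0.5 | 1 - 0.7×0.5 = 65% | 1 - 0.1×0.5 = 95% | 50% |
| b = 0.9 | 1 - 0.7×0.1 = 93% | 1 - 0.1×0.1 = 99% | 90% |

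Even on unwiped skin the fall is 50% or 90% with no sauna effect at all, because baby-wipe cleaning lies between the two wipes in both arms. The within-person change cannot isolate a sauna effect under either placement.

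**3. Comparison between arms at wipe 3, if the sauna only removes surface PAH**

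Ratio, sauna to control = (1-f·e)(1-b)(1-s) / [(1-f·e)(1-b)] = 1-s.

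The study's own wipe cancels. Wipe 2 precedes the draw, and nothing in the protocol makes the placement of wipe 3 differ by arm.

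**4. The same comparison, if the sauna brings PAH to the surface**

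Sections 1 and 2 cite mobilisation of fat-soluble compounds and greater removal of toxic chemicals by the body, so this direction is open too. The effect is then additive. With b = 0.5 and x = 0.05:

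| Patch | Control | Sauna | Ratio |
|---|---|---|---|
| Unwiped | 0.50 | 0.55 | 1.10 |
| Re-wiped, e = 0.3 | 0.7×0.5 = 0.35 | 0.40 | 1.14 |
| Re-wiped, e = 0.9 | 0.1×0.5 = 0.05 | 0.10 | 2.00 |

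The ratio now depends on placement, and the re-wiped patch shows the sauna effect more clearly because less soot is left to mask it. With no sauna effect (x = 0) the ratio is 1 on either patch, so re-wiping creates no false difference between arms.

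**The case for a change.** The case for raising the point is that one sentence would settle it: take wipe 3 in both arms from an adjacent area of equal size. That needs no extra wipes, staff or assays. A sampling instruction belongs in the protocol, and no later analysis can restore removed residue or reconstruct overlap that was never recorded. If the assays are funded, wipes 2 and 3 are an obvious pair to compare. The plan already accepts a change of site between wipes 1 and 2.

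Part of this stands. Both wipes are directed to the same sites on the same side, no unwiped skin is reserved, and the arm and neck locations are loose. Anyone who later reports the fall from wipe 2 to wipe 3 should not read it as an effect of the sauna.

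The rest does not make it an error. No text orders the same patch to be wiped twice; that is an inference, strongest for the calf. The within-person fall would still be confounded by cleaning after the change. The change also has a price: variation between patches enters the comparison of wipes 2 and 3 in at most 24 people, and an additive sauna effect would be diluted by residual soot. Using the right side instead would break the side match and return to skin that was alcohol-wiped before the fire.

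**Conclusion.** The concern does not hold. Followed as written, the plan leaves its stated comparison of sauna with standard treatment free of bias from this source, and neither aim depends on the wipes. What remains is a possible loss of yield in an optional measure, anywhere from 0% to 90% under the assumed removal fractions. Whether that would matter for detection cannot be judged from the protocol. Which placement is better depends on whether the sauna is expected to remove PAH from the skin surface or bring it there, and the protocol does not say. Placing the patch within a site is therefore a choice of sampling technique. This conclusion assumes that wipes are taken in the same way in both arms, as the text directs, and that the fall from wipe 2 to wipe 3 is not itself used as evidence of a sauna effect.
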